Guided Online Care. Guided online care (i.e., self-administered/self-paced, with minimal therapist support) offers a computerized CBT delivery format that reduces therapist demands relative to both office-based care and telehealth, while also affording greater family flexibility, agency, and control. As such, guided online care addresses many of the same logistical care barriers as telehealth, but can also address person-power issues in the mental health workforce, inconsistencies in care quality across practice settings, cost issues, and, for some families, issues of mistrust about working directly with a healthcare professional. Accordingly, self-administered online CBT may in some cases be the preferred treatment mode. CBT lends itself well to standardization to reduce drift and digitization due to its highly structured nature, and digital delivery may be particularly well-suited to youth and younger families who avidly engage with media and technology. That said, attrition can be high in self-administered online care. Increasing studies find some level of minimal/low-intensity human support is often needed to accompany self-administered online CBT—i.e., guided online CBT—to sustain patient motivation, promote adherence, and prevent disengagement.^{67,68} Several very strong self-paced, computerized CBT programs have been developed for the treatment of youth anxiety and controlled trials have shown many of these programs can produce sizeable treatment gains, particularly when administered with some level of guided support.^{51–58}

2.6 Gaps Persist in Understanding How Various Pediatric Anxiety Treatment Formats Perform and Compare in Typical Care Settings.

Despite great promise in the use of technology-based strategies relying on varying levels of therapist involvement to expand the reach of CBT for pediatric anxiety, much remains to be learned about how such modernized CBT formats perform in typical care settings. Similarly, little

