6.2 Outcomes

6.2.1 Primary Outcome Variables. The primary clinical outcomes assessed in the Kids FACE FEARS trial are focused on anxiety symptoms, anxiety-related impairment, treatment responder status, anxiety remission status, and patient-centered outcomes focused on perceived effectiveness and treatment satisfaction. Specifically, these include:

- Youth anxiety symptoms - measured via the PROMIS Pediatric Short Form Item Bank v2.0-Anxiety. The PROMIS pediatric self-report will be completed by children ages 8-18 and parent proxy reports will be complete by guardians for all children. Only parent proxy reports will be collected for children under the age of 8.
- Life interference - measured via the Child Anxiety Life Interference Scale; CALIS
- Treatment Responder Status – measured via the Pediatric Anxiety Rating Scale; PARS
- Family Perceived Effectiveness – measured via caregiver- and youth self-report
- Treatment Satisfaction – measured via caregiver- and youth self-report

6.2.2 Secondary and Exploratory Outcome Variables. Secondary clinical outcomes assessed in the Kids FACE FEARS trial focus on treatment engagement and barriers, broader youth psychopathology (i.e., internalizing problems, externalizing problems, and attention problems), youth sleep difficulties, caregiver internalizing symptoms (i.e., depression symptoms, anxiety symptoms, and stress symptoms), and therapist perceptions of treatment response. Specifically, these include:

- Treatment engagement and barriers – measured via administrative logs, therapist reports, and family reports of: Attendance, Homework engagement, Treatment completion, Child participatory engagement, Caregiver participatory engagement, Comprehension difficulties, Difficulties making time for treatment, Treatment discomfort, Technology treatment challenges, and Therapeutic alliance.
- Youth internalizing problems - measured via the Pediatric Symptom Checklist; PSC-17
- Youth externalizing problems - measured via the Pediatric Symptom Checklist; PSC-17
- Youth attention problems - measured via the Pediatric Symptom Checklist; PSC-17
- Youth sleep problems - measured via a sleep item generated for this study
- Caregiver depression symptoms – measured via the Depression, Anxiety, Stress Scale; DASS-21

- Caregiver anxiety symptoms – measured via the Depression, Anxiety, Stress Scale; DASS-21
- Caregiver stress symptoms – measured via the Depression, Anxiety, Stress Scale; DASS-21

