Treatment responder status. The *Pediatric Anxiety Rating Scale (PARS)*⁷⁹ will be used to independently evaluate clinical significance across the treatment conditions and to benchmark study findings against previously conducted RCTs on youth anxiety.³⁴ The PARS is a well-supported, clinician-rated instrument for assessing the frequency and severity of anxiety symptoms associated with common anxiety disorders in children between the ages of 6 and 17 years.^{79,121} It consists of a 50-item symptom checklist followed by seven global items each rated on a six-point (0-5) scale. Six of the global items are summed to generate a PARS Total Score (range: 0-30). PARS Total Score reductions of 35% or more from baseline to posttreatment are interpreted as reflecting "*PARS Treatment Response*".¹²¹ For the present study, Independent Evaluators (IEs) masked to treatment condition conducted PARS interviews at baseline and at posttreatment with caregivers and youths together and then generated scores based on the pooled information.

Primary patient-centered outcomes. To assess *Caregiver-Perceived Effectiveness*, caregivers will be asked on a 7-point scale at midtreatment and again at posttreatment "How effective do you think the program [has been/was] in treating your child's anxiety?" [0=very ineffective; 3=somewhat effective; 6=very effective]. In addition, caregivers and youth ≥ 8 years will complete a patient-adapted version of the *Clinical Global Impression-Improvement Scale (CGI-I)*¹²² to characterize their judgement of treatment-related improvement, relative to the child's baseline presentation. Consistent with the standard version of the CGI-I, scores of 1 ("very much improved") or 2 ("much improved") will be interpreted as reflecting "*Caregiver-Perceived Treatment Response*" (for caregiver-report) or "*Youth-Perceived Treatment Response*" (for

youth self-report). The caregiver- and youth-report versions of the CGI-I will be administered at midtreatment, posttreatment, and follow-up.

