To assess *Treatment Satisfaction*, caregivers and youth ≥ 8 years will be administered a *Satisfaction Scale* that has them rate three items along 0-3 rating scales at midtreatment and again at posttreatment: “Overall, how satisfied [have you been/were you] with the services that [your family/you] received?” [0=*quite dissatisfied*; 3=*very satisfied*]; “Would you recommend this program to a friend if they [had a child with/had] anxiety?” [0=*no, definitely not*; 3=*yes, definitely*]; and “How pleased [have you been/were you] with how this program has helped [your child/you] with anxiety” [0=*quite displeased*; 3=*very pleased*]. These three items will be averaged for each informant to generate Caregiver Total Satisfaction Scores and Youth Total Satisfaction Scores. For dichotomous interpretation, mean scores ≥ 2 will be interpreted as “Satisfied” and mean scores < 2 will be interpreted as “Dissatisfied.”

7.6.2 Secondary clinical outcomes. Secondary clinical outcomes assessed in the Kids FACE FEARS trial focus on broader youth psychopathology (i.e., internalizing problems, externalizing problems, and attention problems), youth sleep difficulties, caregiver internalizing symptoms (i.e., depression symptoms, anxiety symptoms, and stress symptoms), and therapist perceptions of treatment response. Table 4 presents a summary of the Secondary Clinical Outcomes assessed, which are described in detail below.

Table 4. Secondary Clinical Outcomes in the Kids FACE FEARS Trial

Domain	Measure	Informant(s)	Baseline	Assessment Point		
				After Each Session	Midtreatment	Posttreatment
Broader Youth Psychopathology						
Internalizing problems	Pediatric Symptom Checklist (PSC-17)	C, Y	X	X	X	X
Externalizing problems	Pediatric Symptom Checklist (PSC-17)	C, Y	X	X	X	X
Attention problems	Pediatric Symptom Checklist (PSC-17)	C, Y	X	X	X	X
Youth Sleep Difficulties	Sleep Item	C, Y	X	X	X	X
Caregiver Internalizing Symptoms						
Depression symptoms	Depression, Anxiety, Stress Scale (DASS-21)	CS	X	X	X	X
Anxiety symptoms	Depression, Anxiety, Stress Scale (DASS-21)	CS	X	X	X	X
Stress symptoms	Depression, Anxiety, Stress Scale (DASS-21)	CS	X	X	X	X
Therapist Perceptions of Treatment Response						
Therapist-Perceived Effectiveness	Perceived Effectiveness Scale	T		X		

Therapist-Perceived Improvement	Clinical Global Impression Scale- Improvement	T	X	X
---------------------------------	--	---	---	---

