7.15.4 Retention and Study Compensation

Based on similar studies conducted in usual care settings that do not provide free study treatment, we expect roughly 30-50% attrition by the final follow-up timepoint, and roughly 10% of data points to be missing with each collected timepoint. REDCap surveys will be configured to minimize missing values (e.g., requiring participants to complete each item, or explicitly indicate “refuse to answer” before proceeding to the next item; providing real time alerts to the data management team when items or entire forms are missing). Data will additionally be checked on a weekly basis by a research supervisor, and patterns of missingness will be identified and corrected in real time throughout the study. To further reduce instances of missing data, we have kept the number of study forms to a minimum in order to minimize the burden to participants, and participants will be provided compensation for their time completing study forms. Finally, participants will be compensated for the burdens of completing study assessments (see below).

Given the aim to evaluate treatment engagement and performance under typical circumstances, families are not compensated for participating in treatment. To ensure generalizability and observe the treatment comparators under natural conditions, treatment is not funded by the study nor offered for free. Rather, treatment is to be paid for via the natural channels of payment in the participating health centers (e.g., insurance and co-payments). In contrast, families are compensated for participation in study assessments that are not part of the treatment comparators under study. Specifically, families will receive the following compensations for completing various study assessment components:

- a. \$50 for baseline assessment (staggered payments: \$25 following baseline questionnaires and \$25 following baseline PARS completion)
- b. \$25 for midtreatment assessment
- c. \$50 for posttreatment assessment
 - i. \$30 additional compensation for completing posttreatment PARS assessment
- d. \$100 for completing follow-up assessment

*Coaches (who are not guardians) will not receive compensation for the assessments they complete. Compensation will only be provided to the youth and guardian informants. One ClinCard that will be loaded with the above payments will be given to each family for each child enrolled in the study.

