7.16.3 Covariates

Covariates for each model will include site, language of care, youth age, youth gender, youth race, youth ethnicity, and family resource insecurity (see Measures)

7.16.4 Primary analyses: Comparative effectiveness analyses. For primary analyses on continuous outcomes that were measured across the 4 major timepoints (e.g., caregiver- and youth-reports on the PROMIS Anxiety Scale, CALIS), mixed models of change¹⁴⁴ will be run separately for each outcome. Mixed models are preferred for longitudinal designs because they allow for individual estimates of change and have robust power in the presence of missing data and attrition.^{145,146} Covariates for each model will include site, language of care, youth age, youth gender, youth race, youth ethnicity, and family resource insecurity (see Measures), and any other baseline variables found to significantly differ across participants in the two conditions. The random effects of intercept (reflecting individual variation in mean outcome level) will be assessed. The fixed effects of Treatment Condition, Time, and the Treatment \times Time interaction will be analyzed in the prediction of change. We will examine non-linear models of change (i.e., log transformations of Time), which afford examination of symptom trajectories across time that are not gradual and incremental (e.g., steep improvements during initial weeks of treatment, followed by a slowing down of improvements toward the end of treatment, and then relative stability across the follow-up time interval). To aid interpretation of the meaningfulness of between-group differences, Cohen's d 's will be computed for each continuous outcome on model means at post and follow-up.

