For primary analyses on the dichotomous categorical outcomes PARS Treatment Responder Status at posttreatment, baseline PARS scores will be examined for each participant to determine their individual thresholds for classification as Treatment Responders (i.e., 35% PARS score reduction). These thresholds will be used to classify each participant's statuses as posttreatment. Logistic regression models will examine Treatment Condition (along with the study covariates) as a predictor of Treatment Responder Status and Remission Status at post. For primary analyses on continuous outcomes of Treatment Satisfaction at post, linear regression models will examine Treatment Condition (with the study covariates) as a predictor of caregiver- and youth-reported posttreatment satisfaction.

7.16.5 Heterogeneity of treatment effects. For Aim II analyses (heterogeneity of treatment effects) predictor and moderator terms will be added to the models predicting youth anxiety severity that were outlined above. For study covariates being considered as predictors/moderators (e.g., language of care, youth age, youth gender, youth race, youth ethnicity, and family resource security), this will entail only adding interaction terms, as the main effects of these variables will already be in the models. For the additional variables considered as treatment moderators that are not already included as model covariates (e.g., caregiver nativity) this will entail adding main effects and interaction terms to the models. For each model examining heterogeneity of treatment effects, the relevant terms of interest will be the 2-way interaction of Variable \times Time (reflecting whether the variable uniformly predicted change across the two treatments) and the 3-way interaction of Variable \times Treatment Condition \times Time (reflecting whether the variable moderated treatment effects; i.e., whether the variable predicted differential response across the treatments). As with the Aim I comparative effectiveness analyses, log transformations of Time will be entered to consider non-linear models of change. Significant interactions will be followed up with post-hoc probing on subgroups to clarify the nature and direction of interaction, and results will be plotted for visual depiction.

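### The midtreatment Satisfaction rating enters neither the posttreatment regression nor its imputation model, so missing posttreatment ratings are imputed without their likely best predictor

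*Combined protocol and SAP*

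**What the plan says.** Section 6.2.1 lists as a primary outcome "Treatment Satisfaction – measured via caregiver- and youth self-report". Section 7.6.1 has caregivers and youth aged 8 or over "rate three items along 0-3 rating scales at midtreatment and again at posttreatment", and averages the items into one score per informant.

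Section 7.16.4 reserves mixed models for "continuous outcomes that were measured across the 4 major timepoints", which leaves Satisfaction out. For Satisfaction it states that "linear regression models will examine Treatment Condition (with the study covariates) as a predictor of caregiver- and youth-reported posttreatment satisfaction".

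Section 7.16.2.2 makes all analyses intention-to-treat, with 50 imputed datasets per model. The predictors in the imputation are the other covariates of that model. Sections 7.16.3 and 7.16.4 list these as site, language of care, age, gender, race, ethnicity and resource insecurity; for the mixed models, 7.16.4 adds any baseline variable that differs between arms. Section 7.16.2.4 keeps every randomized participant in the analysis and still sends assessments to families who stop treatment.

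A second primary outcome is "Family Perceived Effectiveness – measured via caregiver- and youth self-report". For it, section 7.6.1 says "caregivers will be asked on a 7-point scale at midtreatment and again at posttreatment", but section 7.16.4 names no model.

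On loss, section 7.15.4 says "we expect roughly 30-50% attrition by the final follow-up timepoint" and expects about 10% of data points missing at each timepoint. Section 2.5 remarks that "attrition can be high in self-administered online care".

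**The concern.** A family that gives a low rating at midtreatment and no rating at posttreatment has already supplied information on this outcome. As written, that information reaches neither the regression nor the imputation. The missing posttreatment value is filled in from arm, site, language and background variables, as if the family resembled the retained families with the same background.

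That is harmless if loss is unrelated to satisfaction, or related in the same way and at the same rate in both arms. Otherwise the retained ratings are selected differently in the two arms and the imputation does not correct for it. At stake is the treatment contrast on a primary outcome for which dissatisfaction is a natural reason not to reply. Some precision is also given up even when loss is harmless.

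**Working it through.** **Plan's own figure.** There is none for this analysis. Only the arm size is taken from section 7.16.1: design effect 1 + (4 − 1) × 0.5 = 2.5, and 60 × 2.5 = 150.

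**Assumptions (none is in the documents).** Ratings are in SD units and bivariate normal, with correlation ρ of 0.4, 0.6 or 0.7 between visits. The true posttreatment difference is 0. Posttreatment ratings are missing for 24% (Therapist-Led) and 37% (Guided Online). Loss follows logit P(missing) = a − s·M, where M is the midtreatment rating. Weak dependence is s = ln 1.5; strong dependence is s = 1, so the odds of loss rise by a factor e per SD lower rating.

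**Formula.** Imputing from arm and from covariates unrelated to the rating leaves each arm's expected mean at the mean of its observed ratings. Hence

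bias (Guided Online − Therapist-Led) = ρ(δ_G − δ_T), with δ = ∫ m φ(m)[1 − expit(a − s·m)] dm / (1 − missing rate).

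Here a is set to give the missing rate. Numerical integration gives δ = 0.095 (24%) and 0.145 (37%) for weak dependence, 0.205 and 0.308 for strong, and 0 for none.

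SE = √(1/114 + 1/94.5) = 0.139, from 150 × 0.76 and 150 × 0.63. Type I error = Φ(−1.96 + bias/SE) + Φ(−1.96 − bias/SE).

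| Dependence on midtreatment rating | δ_G − δ_T | Bias in SD at ρ = 0.4 / 0.6 / 0.7 | Type I error |
|---|---|---|---|
| Equal, weak | 0.050 | 0.020 / 0.030 / 0.035 | 5 to 6% |
| Equal, strong | 0.103 | 0.041 / 0.062 / 0.072 | 6 to 8% |
| Guided Online only, strong | 0.308 | 0.123 / 0.185 / 0.216 | 14 to 34% |
| Therapist-Led only, strong | −0.205 | −0.082 / −0.123 / −0.144 | 9 to 18% |
| Equal, strong, 32% lost in each arm | 0 | 0 | 5% |

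**Variant.** Suppose 10% also lack the midtreatment rating and do not return. Loss among the rated is then (0.24 − 0.10)/0.90 = 15.6% and (0.37 − 0.10)/0.90 = 30%, with strong-dependence δ of 0.137 and 0.253. Bias becomes 0.10 / 0.15 / 0.18 for Guided Online only, −0.05 / −0.08 / −0.10 for Therapist-Led only, and 0.05 / 0.07 / 0.08 for equal strong dependence (type I error up to 9%).

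**Check by actual imputation.** 1,000 simulated trials of 150 per arm, 50 imputations, Rubin's rules, equal dependence in both arms; Monte Carlo error about 0.7 points:

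| ρ, odds ratio per SD, retention | Type I error, covariates only | Type I error, midtreatment rating added |
|---|---|---|
| 0.7, 2, 80% vs 60% | 8.6% (bias 0.085 SD) | 5.5% (bias 0.005 SD) |
| 0.7, 2, 80% vs 70% | 6.9% | 5.3% |
| 0.7, 2, 75% vs 75% | 5.0% | 5.9% |
| 0.5, 1.5, 80% vs 60% | 4.7% | 6.4% |

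The last two rows show no detectable inflation under the plan.

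**Scale.** The difference detectable with 80% power and the SE above is (1.960 + 0.842) × 0.139 = 0.39 SD.

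**Precision under completely random loss of 32%.** 150 × 0.68 = 102 per arm. As planned, SE = √(2/102) = 0.140 and power for 0.35 SD is Φ(0.35/0.140 − 1.96) = 70%. Using the midtreatment rating, SE = √(2[(1 − ρ²)/102 + ρ²/n_mid]). With ρ = 0.4 and n_mid = 135, SE = 0.137 and power is 72%. With ρ = 0.7 and n_mid = 150, SE = 0.129 and power is 78%.

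**The case against.** The strongest reply is that the plan already has a principled missing-data method. A reader might infer that families who leave are discarded and that only satisfied survivors are compared. The documents do not support this: analysis is by intention to treat, every randomized participant is included, and 50 imputed datasets are planned. This part of the reply stands. The family is kept, and only the information in its midtreatment rating is lost. It follows that the posttreatment regression is not wrong in itself, since adding the rating to its imputation model would be enough.

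A reader might also infer that the less-retained arm, presumably Guided Online, will look better than it is. That is not supported either. Section 7.15.4 gives one attrition range for both arms together and none for posttreatment. The remark in section 2.5 is about staying with self-administered care, and leaving treatment is not the same as missing the rating: sections 7.8.2 and 7.16.2.4 keep assessing such families, and section 7.15.4 pays $50 for the posttreatment assessment. If only Therapist-Led loss depends on satisfaction, the bias favours Therapist-Led, the better-retained arm in the example. Equal retention is no guarantee of safety, though: with 30% lost in each arm and strong dependence in Guided Online only, the bias is 0.253ρ, or 0.10 to 0.18 SD.

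The one-arm scenarios are near worst case, and nothing in the documents points to that asymmetry. The near-zero bias after the change is also partly built in, because loss was made to depend on the recorded rating alone. When strong dependence in Guided Online was placed on later dissatisfaction instead, using the midtreatment rating still left 0.17 to 0.26 SD of a 0.31 SD bias.

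Finally, the analyst might include the midtreatment rating in the imputation anyway. The plan does not say so.

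**Conclusion.** The point holds as a specification weakness with a cheap remedy. It does not show that the Satisfaction result will be biased. Bias needs two conditions: loss of the posttreatment rating must depend on earlier dissatisfaction, and it must differ between arms in rate or in strength of dependence. Its direction is then open.

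Under the assumed loss rates and correlations it is about 0.02 to 0.07 SD with equal dependence (0.08 SD at most in the variant). That is small against a detectable difference of about 0.39 SD. Strong dependence confined to one arm gives about 0.1 to 0.2 SD, which would matter. The precision gain is modest, from about 70% to 72–78% power for 0.35 SD.

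The missing model for Perceived Effectiveness is a separate gap in specification. It causes none of this bias, but it belongs in the same revision.

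**What to change.** Either of two changes is sufficient:

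- In section 7.16.4, model Satisfaction with a two-visit repeated-measures model: categorical visit, Treatment × Visit, the study covariates and unstructured covariance, separately for caregiver and youth. The posttreatment contrast stays primary and the midtreatment contrast is reported beside it. State whether the model is fitted by likelihood to the observed ratings or on imputed data; if the latter, both visits must be in the imputation.
- Keep the posttreatment regression and, in section 7.16.2.2, add the midtreatment rating to its imputation model, by arm.

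Use the chosen approach for Caregiver-Perceived Effectiveness too, and name its primary timepoint.

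Add a sensitivity analysis for loss that is not at random, for example by shifting imputed posttreatment ratings downward by a range of amounts, separately by arm. Families lost before midtreatment have no rating to use, and neither change deals with dissatisfaction that arises after midtreatment.

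Cost: plan wording and a little more analysis work, with no new data and no change to the primary contrast. The two-visit model adds a covariance assumption that can be relaxed by arm, and may need a routine other than the lme4 named in the plan.
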